# 4.5.6 Vital Signs, Physical Findings, and Other Observations Related to Safety

### 4.5.6.1 Vital Signs

Vital sign parameter measurements will be summarized by treatment group for each study treatment period. Descriptive statistics will be presented for results and change from baseline at each visit where parameters were scheduled to be collected. Change from the initiation of OLE will also be presented in the Open-Label Extension Period summary.

### 4.5.6.2 12-Lead Electrocardiogram

Twelve-Lead ECG interval parameters will be summarized by treatment group for each study treatment period. Descriptive statistics will be presented for observed values and changes from baseline at each visit where parameters were scheduled to be collected. Change from the initiation of OLE will also be presented in the Open-Label Extension Period summaries.

Twelve-lead ECG will be classified by the investigator as "normal," "abnormal, not clinically significant," or "abnormal, clinically significant." Three-by-three contingency tables will be presented to summarize the shift from the baseline category to the worst post-baseline value of each study treatment period and study overall. Shift from the initiation of OLE value to the worst post-OLE value will also be provided for the Open-Label Extension Period. Summary results will include the count and percentage of subjects within each shift category and treatment group for each study treatment period and study overall.

Prolonged QTc intervals will be summarized as QTc measurements (msec) that are >450, >480, and >500 at each visit where ECG is routinely collected per the clinical study protocol. Change from baseline categories will also be summarized for measurements that represent a change >30 or >60 relative to the baseline value. Change from the initiation of OLE will also be presented in the Open-Label Extension Period summary. Summary results will include the percentage of subjects within each category and treatment group for each study treatment period.

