### **7.1.2. Double-Blind Treatment Period**

The Double-Blind Treatment Period will consist of 5 study visits (Visits 2, 3, 4, 5, and 6 [Day 1 and Weeks 1, 2, 3, and 6]). During this period, all subjects who meet eligibility requirements will be enrolled into the study and randomized to receive double-blind, PO, QD doses of EP547 or placebo for 6 weeks beginning on Visit 2 (Day 1). Subjects will be randomized to receive either 100 mg doses of EP547 or placebo in a 1:1 ratio. Randomization will be conducted centrally via an Interactive Web Response System (IWRS) and stratified based on type of cholestatic disease (PBC, PSC). Visit 2 (Day 1) will not have a visit window; however, for the decentralized model, enrollment/randomization and the first dose of study drug may be separated by up to 10 additional calendar days to allow for home delivery of study drug. When enrollment/randomization and first dose of study drug are on separate days, the first dose of study drug is considered Day 1. All other visits in the Double-Blind Treatment Period will have a visit window of  $\pm 3$  days.

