# 4.1.3 Summarization by Visit

Assessments that are collected only at study visits (i.e., all study assessments except WI-NRS) are to be summarized by study visit and will be based on the nominal, scheduled visit label as reported on the eCRF.

Subjects who discontinue from the study early will have their assessments conducted at the early termination visit mapped and summarized with the next scheduled nominal visit, according to the schedule of events, based on the last visit completed per protocol.

Any subject who completes the Open-Label Extension Period or discontinues study drug (EP547 or placebo) early will complete a Follow-Up Visit (Visit 9) approximately 2 weeks (±3 days) after the last dose of study drug. The Follow-Up Visit may be summarized in both the Double-Blind Treatment Period and Open-Label Extension Period summaries, based on the treatment period of participation at the time of study termination or completion and as warranted by available data.

Data collected at unscheduled visits will not be included in by-visit summaries, but will be considered when endpoint derivations potentially include multiple visits (e.g., determination of baseline value, determination of worst post-baseline value, etc.). All data will be included in subject listings.

For details on WI-NRS analysis visits, see Section 3.4.1.1.

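### The QTc threshold table counts routine-visit ECGs only, so exceedances at unscheduled ECGs, and possibly at some early-termination ECGs, have no by-arm count

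*SAP*

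**What the plan says.** SAP 4.5.6.2 (12-Lead Electrocardiogram) plans three relevant summaries.

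- **Absolute QTc.** Values above 450, 480 and 500 msec are tabulated "at each visit where ECG is routinely collected" under the protocol.
- **QTc change.** "Change from baseline categories will also be summarized for measurements that represent a change >30 or >60 relative to the baseline value". This sentence gives no visit restriction and no worst-value rule.
- **Investigator's overall reading** (normal, abnormal not clinically significant, abnormal clinically significant). Contingency tables "summarize the shift from the baseline category to the worst post-baseline value of each study treatment period and study overall".

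The section closes by saying that percentages of subjects are given by category and arm for each treatment period.

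SAP 4.1.3 (Summarization by Visit) governs unscheduled assessments: "Data collected at unscheduled visits will not be included in by-visit summaries". They "will be considered when endpoint derivations potentially include multiple visits", and the determination of a worst post-baseline value is one of its examples. It also says "All data will be included in subject listings". The same section maps early-termination assessments to the next scheduled nominal visit after the last one completed, and allows the Follow-Up Visit to be shown in the double-blind summaries.

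**The concern.** An unscheduled ECG is usually done because something prompted it, so it is more likely than a routine one to show a prolonged interval. The absolute-threshold table is the place where a reader of the study report looks for QTc outliers by arm, and as specified it leaves those ECGs out. It could show no subject above 500 msec while a listing holds one.

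The SAP does not treat comparable safety data this way. In SAP 4.5.5, laboratory shifts use the worst value over all post-baseline visits, the liver-injury criteria count any instance, and the creatinine criteria count any increase. The investigator's ECG reading also uses the worst value. The QTc thresholds have no such derivation, and no reason is given for the difference.

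**Working it through.** The plan states no figure for this point, so the check is to count scheduled ECGs and then apply the SAP's own rules.

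**1. Scheduled ECGs** (Protocol 9.4.2 to 9.4.5 and Appendix A)

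- Day 1: yes, but dosing follows the listed assessments, so this is the baseline ECG.
- Weeks 1, 2 and 3: none.
- Week 6: yes. Under Protocol 12.7 it is taken before that day's dose when dosing is at the site.
- Week 9: none. Week 12: yes.
- Follow-Up and Early Termination: yes.

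Of the four double-blind visits after Day 1, one has an ECG (0 + 0 + 0 + 1 = 1). A subject who completes the period contributes one scheduled post-baseline double-blind ECG.

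**2. Unscheduled ECGs.** The threshold table is defined by routine visit, so the exclusion in SAP 4.1.3 applies. The exception for derivations spanning several visits does not help, because SAP 4.5.6.2 defines no such derivation for the absolute thresholds. The table counts none of these ECGs.

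**3. Early-termination ECGs.** Under the mapping rule in SAP 4.1.3:

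- last completed visit Day 1, Week 1 or Week 2: mapped to Week 1, 2 or 3, where ECG is not routine, so the ECG may be left out of the table;
- last completed visit Week 3: mapped to Week 6, so the ECG is counted.

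SAP 4.6 plans 29 subjects per arm with at least 26 completers, which allows for 29 − 26 = 3 early withdrawals per arm. How many of them would leave before the Week 3 visit is not stated, so the number affected by this mapping is 0 to 3 per arm under that plan.

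**4. Change categories.** The sentence on changes above 30 and 60 msec fits two programs: one that counts by visit, like the sentence before it, and one that counts subjects over the whole period, as the closing sentence could suggest. The SAP does not choose between them.

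**5. Weight of one subject.** SAP 4.1.1 sets denominators to subjects with available data unless otherwise noted, so both planned figures are shown:

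- 1/29 = 3.4 percentage points, if all randomized subjects in the arm have data;
- 1/26 = 3.8 percentage points, if only the planned completers do.

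The documents give no basis for the number of unscheduled ECGs, so no total understatement can be computed.

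**The case against.** The strongest reply is that little is lost. Unscheduled ECGs are listed, and with about 58 subjects a listing can be read line by line. They can enter the worst-value shift table of the investigator's reading. A clinically significant ECG finding may be recorded as an adverse event, and those tables are not limited to scheduled visits; events of Grade 3 or higher also go to the Data Monitoring Committee. QTc is not the event of special interest here (acute kidney injury is), and the protocol's risk text describes a low electrophysiologic risk. The protocol names no symptom-triggered ECG, so the number of affected subjects may be zero. A table limited to scheduled ECGs also has the merit of equal ascertainment in both arms, whereas event-triggered ECGs may not be obtained equally.

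Most of this stands, and it sets the priority. It does not remove the gap: a listing is not a by-arm count, the investigator's reading carries no msec thresholds, and an adverse event depends on a judgement of clinical significance.

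A reader might go further and infer that QTc prolongation at an unscheduled ECG is never counted in any QTc summary, or that the table understates the true incidence by some known amount. The documents support neither. The visit restriction is attached to the absolute thresholds only, and the change categories are ambiguous rather than restricted. Subjects who stop early have termination and follow-up ECGs, some of which can enter the double-blind tables. The sparse schedule is a design choice that a new row would not alter, and a row mixing routine and prompted ECGs would not measure true incidence either.

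**Conclusion.** The point holds for the absolute thresholds. Under SAP 4.5.6.2 and 4.1.3 read together, a QTc above 450, 480 or 500 msec at an unscheduled ECG is not counted in the threshold table, and for completers the double-blind part of that table rests on the Week 6 ECG. Omission of termination ECGs mapped to Weeks 1 to 3 is possible on a literal reading but not certain. The change categories need clarifying.

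The size is not known. The per-subject weights above assume the planned arm sizes; the number of subjects to multiply them by may be zero. This is a modest improvement to a safety display. No efficacy result, stopping rule or committee trigger depends on the table.

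**What to change.** In SAP 4.5.6.2, keep the by-visit rows and add an any-post-baseline row for each treatment period and for the study overall. It should cover QTc above 450, 480 and 500 msec and change above 30 and 60 msec, and take each subject's worst value over all post-baseline ECGs, including unscheduled and early-termination ones. State the denominator, for example subjects with at least one post-baseline ECG in the period, and say whether the by-visit change categories use routine visits only. SAP 4.1.3 already allows unscheduled data in a worst-value derivation, so that section needs no change.

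The cost is a few lines of SAP text and one block in an existing table, with no new data collection. Because prompted ECGs may be obtained unequally between arms, a table note should say that the new row is to be read alongside the by-visit rows.

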#### 4.5.6.3 Physical Examination

Any clinically significant findings from the physical examination assessment will be reported on the Medical History form (prior to first dose) or Adverse Events form (post first dose). A separate subject listing of physical examination results will not be provided.

### 4.5.6.4 Crohn's Disease Activity Index (Crohn's Disease Subjects Only)

Crohn's Disease Activity Index total criteria point counts will be summarized by treatment group for each study treatment period for the subset of study subjects with CD. Descriptive statistics will be presented for results and change from baseline at each visit where parameters were scheduled to be collected. Change from the initiation of OLE will also be presented in the Open-Label Extension Period summary.

Additionally, the assignment of the CDAI scores into the disease severity categories of "asymptomatic remission (CDAI <150)," "mild-to-moderate CD (150 to 219)," "moderate-to-severe CD (220 to 450)," and "severe-fulminant disease (>450)." Four-by-four contingency tables will be presented to summarize the shift from the baseline category to the Week 6 and Week 12 categories (Open-Label Extension Period summary) for each study treatment period. For the Open-Label Extension Period summary, change from initiation of OLE to Week 12 will also be provided. Summary results will include the count and percentage of subjects within each shift category and treatment group for each study treatment period.

# 4.5.6.5 Partial Mayo Scoring Index (Ulcerative Colitis Subjects Only)

The Partial Mayo Scoring Index questionnaire categories (Bleeding, Stool Frequency, and Physician Assessment) and the total index score will be summarized by treatment group for each study treatment period for the subset of study subjects with Ulcerative Colitis. Summary results will include the count and percentage of subjects within each shift category and treatment group for each study visit where the questionnaire was collected.

Additionally, the total index score will be summarized as four-by-four contingency tables to present the shift from the baseline category to the Week 6 and Week 12 categories (Open-Label Extension Period summary) for each study treatment period. For the Open-Label Extension Period summary, change from Initiation of OLE to Week 12 will also be provided. Summary results will include the count and percentage of subjects within each shift category and treatment group for each study treatment period.

### 4.5.6.6 Prior and Concomitant Medications

Medications will be coded using the World Health Organization (WHO) Drug Global B3, version March 2022. Medications entered on the eCRF will be mapped to Anatomical Therapeutic Chemical (ATC) drug class (level 4) and drug name. The ATC drug class level 3 term is provided if level 4 is not available, and the ATC drug class level 2 term is provided if level 3 and level 4 are not available.

Prior and concomitant medications will be summarized separately and the study phase of each medication will be determined programmatically based on medication start and end dates. A prior medication is defined as any medication administered prior to the date of the first dose of study drug. A concomitant medication is defined as any medication administered on or after the date of the first dose of study drug. A medication may be defined as both prior and concomitant, and may occur in both study treatment periods based on reported start and end dates. If it cannot be determined whether a medication was received prior to the start of study drug dosing due to partial or missing medication start and/or end dates, it will be considered a prior medication. Likewise, if it cannot be determined whether a medication was received after the start of study drug dosing, it will be considered concomitant.

For both prior and concomitant medications summaries, the number and percentage of subjects receiving any medication will be summarized by treatment group, as will the number and percentage receiving any medication by ATC drug class and generic drug name. Concomitant medications will be summarized separately for the Double-Blind Treatment Period and Open-Label Extension Period. Prior medications will be summarized for the Full Analysis Set. Subjects reporting use of more than one medication at each level of summarization (any medication received, ATC class, and generic drug name) will be counted only once. The ATC class terms will be displayed by descending order of incidence, as will generic drug names within each ATC class. Subjects receiving UDCA as part of their allowed treatment regimen will have the medication reported on the Prior and Concomitant Medication CRF for summarization in each applicable table. The study phase during which each medication was received (e.g., prior, concomitant, or both) will be presented on the listing of prior and concomitant medications, as well the study treatment period in which the medication

was received (e.g., Double-Blind Treatment Period, Open-Label Extension Period, or both). A listing of those concomitant medications that are prohibited and/or rescue medications and are to be considered intercurrent events for the primary estimand will also be provided.

# 4.6 Determination of Sample Size

Assuming a standard deviation of 2.5 points, a sample size of 26 subjects per treatment group provides approximately % power to detect a EP547 and placebo with respect to the change in weekly mean of the daily WI-NRS score based on a 2-sided, 2-sample comparison of means at the 5% significance level. With an anticipated early withdrawal rate of approximately 10%, the planned enrollment of 29 subjects per treatment group will ensure that at least 26 subjects complete the 6 weeks of double-blind treatment.

## 4.7 Changes in the Conduct of the Study or Planned Analyses

There were no changes to the study conduct or planned analyses identified within the development of this SAP, relative to the descriptions provided within the clinical study protocol.

